8.1.1. Incidence of Adverse Events

An overview summary of TEAEs will be provided and will include the following

- Participants with at least 1 TEAE
- Participants with at least 1 TEAE related to study drug
- Participants with at least 1 TESAE
- Participants with at least 1 TESAE related to study drug
- Participants who drug withdrawn due to TEAE
- Participants who drug withdrawn due to TEAE related to study drug

The frequency of TEAEs will be tabulated by SOC and PT.

8.1.2. Relationship of Adverse Events to Study Drug

The relationship between the study intervention and each occurrence of each AE or SAE is assessed by the Investigator. The relationship will be classified as Related or Not Related.

The frequency of TEAEs will be tabulated by SOC, PT and by relationship.

8.1.3. Intensity of Adverse Event

The Investigator will make an assessment of intensity for each AE and SAE reported during the study and assign it to one of the following categories from National Cancer Institute Common Terminology Criteria for Adverse Events (CTCAE) v5.0, published 27 Nov 2017:

- Grade 1: Mild (awareness of sign or symptom, but easily tolerated)
- Grade 2: Moderate (discomfort sufficient to cause interference with normal activities)

- Grade 3: Severe (incapacitating, with inability to perform normal activities)
- Grade 4: Life-threatening
- Grade 5: Fatal

The frequency of TEAEs will be tabulated by SOC and PT and by intensity.

8.1.4. Serious Adverse Events

Serious adverse events (SAEs) will be analyzed in terms of TESAEs which are defined as any SAEs that begin or worsen on or after the first dose of treatment until the EOS or ET.

An SAE is defined as any untoward medical occurrence that at any dose:

- Results in death
- Is life-threatening
- Requires participant hospitalization or prolongation of existing hospitalization
- Results in persistent disability/incapacity
- Is a congenital anomaly or birth defect
- Other situations

The frequency of TESAEs will be tabulated by SOC and PT, and by SOC and PT and by relationship.

Treatment-emergent SAEs will be listed separately.

8.1.5. Adverse Events Leading to drug withdrawal

Treatment-emergent AEs leading to drug withdrawal will be listed separately.

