### 6.6. Dose Modification

Not applicable. ALXN1840 and celecoxib will be administered as single doses in the prescribed parts of the study.

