#### 9.4.2. Safety Analyses

All safety analyses will be performed on the Safety Set.

Safety analyses will include an analysis of all AEs, ECGs, clinical laboratory data, physical examinations, and vital sign measurements using descriptive statistics. Data will be summarized by study groups.

No inferential statistical analyses are planned for the safety parameters of this study. The incidence of AEs and SAEs will be summarized by System Organ Class (SOC) and Preferred Term for each treatment and overall, and by relationship to study intervention. Adverse events will also be summarized by treatment and overall by severity. Serious AEs and AEs resulting in withdrawal from the study will be listed. Participants having multiple AEs within a category (eg, overall, SOC, Preferred Term) will be counted once in that category. For severity tables, a participant's most severe event within a category will be counted.

Changes from baseline in vital sign measurements and laboratory assessments (eg, chemistry, blood cell count with differential, and urinalysis) will be summarized by study groups. Laboratory parameter values will be graded according to the National Cancer Institute Common Terminology Criteria for Adverse Events (CTCAE). Shift tables by treatment will be produced for these laboratory parameters. These tables will summarize the number of participants with each baseline grade relative to the reference ranges and changes to the worst highest grade assessed post-dose during the study.

Electrocardiogram parameters will be measured at the specified time points, including heart rate, PR, RR, QRS, QT, and corrected QTcF intervals. The average of the triplicate ECG readings at the time points collected will be calculated, and changes from pretreatment baseline values will be assessed by each treatment.

All concomitant medications will be coded and summarized using the World Health Organization (WHO) Drug Dictionary.

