3.1. Overall Study Design and Plan

The study is being conducted as a randomized, 2-period, 2-sequence, cross-over study to determine the effect of a single dose of ALXN1840 (perpetrator) on the single dose celecoxib (victim) kinetics in healthy male and female participants.

The study has a Screening period (Day -28 to Day -2), two 11-day study periods (Day 1 to Day 11) with a minimum of 14 days between doses of celecoxib, and an End of Study (EOS) Visit (Day 15 ± 2 days) after Period 2 dosing. Participants will report to the clinical research unit (CRU) on the day prior (Day -1) to both dosing periods.

All participants will receive 1 treatment in each study period; treatment order will be defined based on randomization:

- Treatment A: One 200 mg celecoxib capsule with 240 mL water (fasting).
- Treatment B: One 200 mg celecoxib capsule $+ 4 \times 15$ mg ALXN1840 entericcoated (EC) tablets with 240 mL water (fasting).

Based on randomization, participants will be administered either Treatment A or Treatment B in each period. A wash-out period of at least 14 days must separate dose administration in Period 1 and Period 2. Participants will remain institutionalized from the day prior to dosing until Day 11 following dose administration for each period.

The PK profile of ALXN1840 and celecoxib will be determined by blood sampling following single dose administration over approximately 5 half-lives or more for both study interventions. Blood sampling for PK assessments will occur at pre-dose, 1, 2, 3, 4, 5, 6, 8, 12, 24, 48, 72, 96, 120, 144, 168, 192, 216, 240, and 336 hours post-dose to ensure full assessment of exposure over time. The nominal 336-hour sample for Period 1 is pre-dose sample for Period 2. In addition to PK sampling, safety and tolerability will be assessed by monitoring adverse events (AEs), vital signs, 12-lead electrocardiograms (ECGs), and laboratory parameters.

Following scheduled procedures on Day 11, participants will be discharged from the unit. If there are any participants with clinically significant abnormalities at the time of discharge, the Investigator should notify the Medical Monitor prior to discharge, and participants may be asked to remain institutionalized for further clinical monitoring.

Participants may be asked or required to stay in the CRU between Periods 1 and 2, and/or before the EOS visit, for their own safety, and also to maintain the integrity of the conduct of the study.

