3.2. Schema

[figure not shown]

Figure 1:Study ALXN1840-HV-105 Schematic

Participants will be admitted on Day -1 of each period for Check in procedures. Eligible participants will be randomized on Day 1 immediately prior to dosing in Period 1.

Participants will receive treatment (A or B) based on randomization on Day 1 of each period. Blood samples for PK analysis of total Mo (as a measure of ALXN1840) and celecoxib will be collected in each period on Day 1 at pre-dose, 1, 2, 3, 4, 5, 6, 8, 12 and 24 hours (Day 2) and then at 24 hour intervals on Days 3, 4, 5, 6, 7, 8, 9, 10, and Day 11. The nominal 336-hour sample for Period 1 will be collected pre-dose in Period 2. Participants will be discharged on Day 11 of each period after completion of all procedures and review of all safety data. The end of study visit (EOS) will occur on Day 15 ± 2 of Period 2, with the collection of 336-hour PK sample for Period 2.

Participants may be asked or required to stay in the CRU between Periods 1 and 2, and/or before the EOS visit, for their own safety, and also to maintain the integrity of the conduct of the study.

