5.1. Disposition

Using the enrolled set, the screen failure of participants will be summarized with counts and percentages by overall. Summary table will include the following:

- Number of participants in the enrolled set (ie, all participants who signed the ICF)
- Number of participants who were screen failures
- Number of participants who were randomized
- Number of participants who failed screen due to COVID-19 related reasons
- Reason for screen failure that was not due to eligibility

Based on the randomized participants, the analysis sets will be summarized with counts and percentages by treatment and overall. Summary table will include the following:

- Number of participants included in PK/PD analysis set
- Reason for exclusion from the PK/PD analysis set
- Number of participants included in safety set
- Reason for exclusion from the safety set

Using the randomized participants, PK analysis set, and safety set respectively, the disposition of participants will be summarized with counts and percentages by treatment and overall. Summary table will include the following:

• Number of participants who completed the study

- Number of participants who discontinued the study
- Reasons for discontinuation
- Number of participants who discontinued the treatment
- Reasons for treatment discontinuation
- Number of participants who were discontinued due to COVID-19

Screen failure data, participant disposition data, and analysis set will be presented in separate data listings for the participants who randomized.

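### The SAP counts and lists TEAEs leading to drug withdrawal where the protocol promises a listing of AEs that end study participation, so an AE-driven exit after the Period 2 dose may be missed

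*SAP*

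**What the plan says.** Protocol 9.4.2 (Safety Analyses) states: "Serious AEs and AEs resulting in withdrawal from the study will be listed".

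SAP 8.1.5 states: "Treatment-emergent AEs leading to drug withdrawal will be listed separately". The overview table in SAP 8.1.1 has two related rows, "Participants who drug withdrawn due to TEAE" and "Participants who drug withdrawn due to TEAE related to study drug". No AE output in the SAP is specified in terms of leaving the study. SAP 11 declares one change from the protocol, the definition of the PK/PD analysis set, and does not mention this one.

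On dosing, Protocol 6.6 says "ALXN1840 and celecoxib will be administered as single doses in the prescribed parts of the study", and SAP 3.1 gives one treatment per period over two periods. On follow-up, SAP 3.2 says "The end of study visit (EOS) will occur on Day 15 ± 2 of Period 2".

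Outside the AE section, SAP 5.1 tabulates "Number of participants who discontinued the study", with reasons, by treatment and overall, separately from discontinuation of treatment.

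**The concern.** The protocol and the SAP name two different events, and these documents treat them as different. Protocol 7.1 has a participant whose study intervention is stopped stay on for safety follow-up. SAP 5.1 gives study discontinuation and treatment discontinuation separate lines.

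The difference matters because of the single-dose design. In Period 1, the only drug that can be withdrawn is the Period 2 dose. After the Period 2 dose there is none, yet AEs are collected up to the end-of-study or early-termination visit. A participant who leaves because of an AE in that interval meets the protocol's description but, on ordinary meaning, not the SAP's.

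Safety and tolerability of ALXN1840 with celecoxib is a secondary objective, and Protocol 9.7 has the ad hoc Safety Review Committee convene within 24 hours when a participant is withdrawn because of an adverse reaction. An exit serious enough to trigger that meeting could leave a zero in the AE overview and no entry in the dedicated listing.

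**Working it through.** **1. Which exits each wording reaches**

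| Situation | Protocol 9.4.2 listing | SAP 8.1.1 and 8.1.5 (ordinary meaning) |
|---|---|---|
| AE in Period 1; participant leaves before the Period 2 dose | Yes | Yes |
| AE in Period 1; Period 2 dose not given; participant stays for follow-up | No | Yes |
| AE after the Period 2 dose; participant leaves before the end-of-study visit | Yes | No |

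The third row is the gap. It is open from Period 2 Day 1 to Day 15 ± 2, which is Day 13 to Day 17, or 12 to 16 days after dosing.

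**2. Inputs for the size**

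- Planned enrolment is 38, with 19 in sequence AB and 19 in sequence BA (SAP 3.1, Table 1).
- The plan's figure reproduces from 32 evaluable participants and 15% dropout (SAP 4.2): 32 / (1 − 0.15) = 37.6, rounded up to 38.

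**3. Share of dosings in Period 2, as planned**

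- All dosings: 38 × 2 = 76; Period 2 has 38; 38 / 76 = 50%.
- Treatment B (celecoxib + ALXN1840): sequence AB receives it in Period 2; 19 / 38 = 50%.
- Treatment A (celecoxib alone): sequence BA receives it in Period 2; 19 / 38 = 50%.

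**4. Sensitivity to losses before Period 2**

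Assume a fraction d of sequence AB leaves before Period 2, with no replacement. The Period 2 share of Treatment B dosings is 19(1 − d) / [19(1 − d) + 19].

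- d = 5%: 18.05 / 37.05 = 48.7%.
- d = 15%: 16.15 / 35.15 = 45.9%.

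The same formula applies to Treatment A in sequence BA. The range 5% to 15% is an assumption; the SAP's 15% covers dropout from all causes and at any time.

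These are shares of dosings exposed to the gap. They are not shares of events, for which the documents give no rate.

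**The case against.** The strongest reply is that the data stay in the report. SAP 5.1 counts study discontinuations with reasons and lists disposition, SAP 8.1 lists all AEs to the end-of-study or early-termination visit, and the TEAE tables give SOC, preferred term, relationship and intensity. With 38 participants, anyone reading the disposition and AE listings together could identify a case. This stands and limits the consequence. It does not supply the listing that the protocol promised, because no specified output links the AE to the exit.

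Several stronger readings are tempting, but the documents do not support them:

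- *The SAP criterion cannot capture any exit after Period 2 dosing.* The SAP leaves the term undefined, and Protocol 7.2 treats a participant who leaves the study as discontinued from study intervention too. Such an exit might be coded as drug withdrawal. The result then depends on an unstated coding choice, which is itself a reason to define the term.
- *The reports are biased in favour of ALXN1840.* The gap covers 19 of 38 planned dosings under each treatment. What is shown is possible under-reporting that depends on the period in which a treatment is given.
- *The count is understated by about half.* That needs both the narrow reading of the term and equal exit risk after each dose. No event rate is given, and Protocol 7.2 expects withdrawal to be uncommon.
- *A secondary endpoint has been changed.* The safety endpoints are TEAE and TESAE incidence, physical examination, vital signs, laboratory and ECG results. AE withdrawals are not among them. The protocol asks only for a listing, so the overview rows are an addition in the SAP.

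The SAP wording also has a use: it catches the second row of the table, which the protocol wording misses. Both items should be kept.

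**Conclusion.** The listing in SAP 8.1.5 departs from Protocol 9.4.2 without being declared, and the overview in SAP 8.1.1 follows the same narrower criterion. On the ordinary meaning of drug withdrawal, AE-driven exits after the Period 2 dose fall outside both outputs. That window follows 38 of 76 planned dosings, and 19 of 38 under each treatment (45.9% to 48.7% of a treatment's dosings if 15% to 5% of the relevant sequence is lost beforehand).

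The consequence is a possible false zero in two AE outputs. It is not a loss of data and not a demonstrated difference between treatments. The number of participants affected is likely to be small and may be none. The primary PK analysis is untouched. The conclusion rests on the ordinary reading of an undefined term and on the planned 19 + 19 allocation.

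**What to change.** - **SAP 8.1.5:** list TEAEs resulting in withdrawal from the study, as Protocol 9.4.2 requires, each assigned to the most recent treatment under the rule already in SAP 8.1.
- **SAP 8.1.1:** add two rows for participants with a TEAE leading to study withdrawal, one for any and one for related.
- **Drug withdrawal:** keep it as a separate row, defined for reporting purposes as the Period 2 dose not given.
- **SAP 11:** record any difference from the protocol that remains.

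The cost is SAP wording and one derived flag. The reason for discontinuation is already to be recorded on the CRF (Protocol 7.2), and AEs are collected to the end-of-study or early-termination visit. No new data and no protocol amendment are needed.

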8.2. Clinical Laboratory Evaluations

Laboratory assessments (including chemistry, hematology, and coagulation) will be performed at Screening, Check-in for each period, Day 2 for each period, Day 5 for each period, Day 10 for each period, and EOS or ET.

Urinalysis will be performed at Screening and Check-in for each period.

Summary statistics and change from baseline for chemistry, hematology, and coagulation will be presented by treatment and by visit. Laboratory parameter values will be graded according to the National Cancer Institute CTCAE. Shift tables will be produced for chemistry, hematology, and coagulation. Shift from baseline grade relative to the reference ranges tables will be presented by treatment and by visit. Shift from changes to the worst highest grade assessed post-dose during the study tables will be presented by treatment. Last recheck values collected prior the dose of treatment will be used as baseline and all rechecks will be deleted from post-dose observations in calculating summary statistics.

All clinical laboratory tests (including chemistry, hematology, coagulation, and urinalysis) will be presented in data listings.

8.2.1. Chemistry

Serum chemistry evaluation will include blood urea nitrogen, potassium, bicarbonate, sodium, glucose, aspartate aminotransferase, alanine aminotransferase, chloride, alkaline phosphatase, direct bilirubin, total bilirubin, albumin, creatinine, and creatine phosphokinase.

8.2.2. Hematology

Blood hematology evaluation will include platelet count, red blood cell (RBC) count, hemoglobin, hematocrit, RBC indices (including mean corpuscular volume, mean corpuscular hemoglobin, and % reticulocytes), and white blood cell count with differential (including neutrophils, lymphocytes, monocytes, eosinophils, and basophils).

8.2.3. Coagulation

Blood coagulation evaluation will include international normalized ratio, partial thromboplastin time, and prothrombin time.

8.2.4. Urinalysis

Urinalysis evaluation will include specific gravity, pH, glucose, protein, blood, bilirubin, urobilinogen, nitrite, leukocyte esterase by dipstick, and microscopic examination.

8.3. Vital Sign Measurements

Oral temperature, pulse rate, respiratory rate, and systolic and diastolic blood pressure (mm Hg) will be performed at Screening, Day 1 (Pre-dose, 1 Hour, 4 Hour, 8 Hour, and 12 Hour) for each period, Day 2 (24 Hour) for each period, and EOS or ET.

Weight will be collected at Screening and Check-in for each period. BMI will be collected at Screening only.

Blood pressure and pulse measurements should be preceded by at least 5 minutes of rest for the participant in a quiet setting without distractions (eg, television, cell phones).

Summary statistics and change from baseline for vital signs (temperature, pulse rate, respiratory rate, and systolic and diastolic blood pressure) will be presented by treatment and overall and by visit and time point. Last recheck values collected prior to the dose of treatment will be as baseline and all rechecks will be deleted from post-dose observations in calculating summary statistics.

Vital sign measurement results, including height, weight, and BMI, will be presented in a data listing.

8.4. Physical Examination

A full PE, at a minimum, assessments of the cardiovascular, respiratory, gastrointestinal, and neurological systems will be performed at Screening, Check-in for each period, and EOS or ET. A symptom-driven physical examination may be performed at other times, at the principal investigator's discretion.

General appearance, skin, head/ear/eye/nose/throat, neck, lymph node, chest, heart, abdominal cavity, limb, central nervous system, and musculoskeletal will be captured on the CRF.

Physical examination results will be presented in a data listing.

8.5. Electrocardiogram

Triplicate 12-lead ECG will be performed at Screening and Day 1 (Pre-dose and 4 Hour [before lunch]) for each period.

Participants will be resting in the supine position for at least 15 minutes prior to and 5 minutes after each nominal time point for ECG extraction.

Heart rate, PR interval, QRS interval, RR interval, QT interval, QT interval corrected for heart rate using Fridericia's formula (QTcF), and interpretation of ECG will be captured on the CRF.

The average of the triplicate ECG readings at the time points collected will be calculated. Summary statistics and change from baseline of calculated average for heart rate, PR interval, QRS interval, RR interval, QT interval, and QTcF interval will be presented by time point. Last recheck values collected prior to the dose of treatment will be as baseline and all rechecks will be deleted from post-dose observations in calculating summary statistics.

Triplicate 12-lead ECG findings will be presented in a data listing.

8.6. Other Safety Data

8.6.1. Liver Function Results

All events of ALT \ge 3 \times upper limit of normal (ULN) and bilirubin \ge 2 \times ULN (\ge 35% direct bilirubin) or ALT \ge 3 \times ULN and international normalized ratio (INR) \ge 1.5, if INR measured which may indicate severe liver injury (possible Hy's Law), must be reported as an SAE (excluding studies of hepatic impairment or cirrhosis).

Liver function results will be presented in a summary table and eDISH (evaluation of drug-induced serious hepatotoxicity) plots.

8.6.2. Serology

Serology including HIV, hepatitis B, and hepatitis C screen will be performed at Screening.

Serology results will be presented in a data listing.

8.6.3. Pregnancy Test

Serum or urine pregnancy test for female participants and female spouses/partners of male participant will be performed at Screening, Check-in for each period, and EOS or ET.

Pregnancy test results will be presented in a data listing.

8.6.4. Follicle Stimulating Hormone

Follicle stimulating hormone (FSH) will be performed at Screening and only needed if claiming exemption from contraception requirement due to menopause.

FSH results will be presented in a data listing.

8.6.5. Discussion/documentation of contraception method

Discussion/documentation of contraception method will be performed at Screening and Check-in for each period. The discussion/documentation of contraception method results will be kept in the source documents and will not be recorded on the CRF; therefore, the discussion/documentation of contraception method results will not be presented in any of the tables, listings, or figures.

8.6.6. Retained Sample

A single 12 mL sample will be retained for evaluation in the event of an unexpected safety finding; retained samples may be destroyed after completion of the clinical study report. The retained serum sample will only be collected pre-dose on Day 1 of Period 1.

Retained sampling results will be presented in a data listing.

9. Pharmacokinetics and Pharmacodynamic Analysis

9.1. Pharmacokinetic Sampling

Whole blood samples will be collected for the measurement of plasma concentrations of total Mo, PUF Mo, and celecoxib at the following time points: pre-dose and post-dose at 1, 2, 3, 4, 5, 6, 8, 12, 24, 48, 72, 96, 120, 144, 168, 192, 216, 240, and 336 hours in each period. Additional samples may be collected at additional time points during the study if warranted and agreed upon between the Investigator and Alexion. Collection of samples for PK evaluation should occur as close as possible to the scheduled time and actual time of collection should be documented on the eCRF. Samples collected within $\pm 10\%$ of the scheduled time, or 30 minutes, whichever is less, will not be considered a protocol deviation. In the event of a safety occurrence and after agreement between the Investigator and Medical Monitor, up to 3 additional PK sampling timepoints may be added.

PK samples will also be used for the PD analysis of total Cu and PUF Cu.

